**CLINICAL STUDY SUMMARY**

Title	Phase IIb Study of Intramyocardial Injection of Autologous Umbilical Cord Blood Derived Mononuclear Cells during Stage II Surgical Repair of Hypoplastic Left Heart Syndrome (AutoCell-II)
Running Title	Phase IIb Efficacy Study of UCB-MNC Intramyocardial Injection for HLHS and HLHS Variants
Protocol Number	CSP-4401
Phase	Phase IIb
Study Design	Prospective, Open label, Non-randomized, Observational Study
Overall Study Duration	6 years
Subject Participation Duration	Up to 4 years or until pre-operative work-up for Stage III surgical palliation has been completed or until cardiac transplant, whichever is first
Single or Multi-Site	Multi-Site
Objectives	This study will evaluate the efficacy and safety of UCB-MNC intramyocardial injections performed during Stage II surgical palliation by focusing on short and long-term cardiac function leading up to the pre-operative work-up for Stage III surgical palliation.
Study Purpose	Determine if the delivery of the autologous UCB-MNC product into the myocardium of the right ventricle of the heart at the time of Stage II surgical repair will provide a short-term improvement in cardiac function, while also providing a reduction in the cumulative days of hospitalization following Stage II surgical repair. Additionally, long-term improvement in cardiac function, growth, reaching Stage III surgical repair pre-op work-up and prolonging time to cardiac transplantation or death will be determined. Reaching developmental milestones and quality of life will also be monitored.
Number of Subjects	30-50 treated subjects receiving cell product, along with 30-50 subjects with standard surgical treatment (not receiving cell product).
Study Population	Subjects less than 13 months of age with HLHS or HLHS variant who are undergoing Stage II surgical palliation.
Study Product, Dose, Route, Regimen	The investigational product is autologous MNC derived from UCB at a concentration of 10-30 million TNC per mL. The investigational product will be delivered into the right myocardium via sub-epicardial injections of 0.1 mL per kg body weight to achieve the target dose of 1-3 million TNC per kg body weight.
Time and Duration of Administration	A single treatment will be administered intraoperatively upon the successful completion of the planned Stage II surgical repair.

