This protocol is designed to evaluate the clinical outcomes following intramyocardial delivery of autologous UCB-MNC and is being conducted to investigate this product and its delivery procedure as a potential new therapy to strengthen the right ventricle of patients with HLHS or HLHS variants. The central hypothesis of this study is that the delivery of the autologous UCB-MNC product into the myocardium of the right ventricle of the heart at the time of Stage II surgical repair will provide a short-term improvement in cardiac function, reaching growth and developmental milestones, and quality of life, while also providing a reduction in the cumulative days of hospitalization following discharge for the Stage II surgical repair. It is also hypothesized that the autologous UCB-MNC product and its delivery procedure will ultimately provide long-term improvement in cardiac function, reaching growth and developmental milestones, reaching Stage III surgical repair pre-operative work-up, prolonging time to cardiac transplantation or death, and improving quality of life.

The safety and efficacy endpoints will be evaluated by the DSMB at least annually. This will determine the appropriateness of continued enrollment in both arms of this Phase IIb study. By demonstrating reasonable efficacy and safety of this product and its delivery procedure in this study, future definitive studies may be designed with the goal to establish a marketable regenerative therapy to treat this rare, life-threatening congenital heart disease as quickly as possible.

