The feasibility of the Phase I study was most significantly compromised by the study inclusion and exclusion criteria. One in every six acceptable autologous products was administered during the Stage II surgery based largely on the narrow Phase I study eligibility criteria. The Phase IIb study has been designed to address the feasibility issue identified in Phase I by requiring fewer exclusion criteria for subject enrollment. It is anticipated that one out of every two subjects with manufactured autologous product will be eligible for enrollment in the treatment arm of this Phase IIb study. Therefore, treating up to fifty subjects under this Phase IIb study should be feasible within a 5-7 site clinical trial.

The feasibility of the Observational study that required prospective data collection for control subjects proved to be highly problematic as recruitment was limited to only three subjects in this time period. The primary limitation to recruitment was in part the bias for eligible subjects to choose to participate in the treatment study. Only a few subjects that met all eligibility criteria and had available UCB product decided to not participate in the Phase I cell-delivery study. Additionally, a significant number of subjects that did not have available autologous product and met all eligibility criteria of the Observational study were unwilling to participate in the Observational study that required multiple non-standard of care clinical visits with additional blood and imaging studies. Therefore, the Phase IIb study was designed with fewer non-standard of care clinical visits to address the feasibility of recruiting a proper control cohort.

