## 3 STUDY DESIGN

### 3.1 General Design

This Phase IIb study is a multicenter, prospective, open-label, non-randomized, observational study designed to evaluate the efficacy and safety of UCB-MNC delivered into the right ventricular myocardium of subjects with HLHS or HLHS variants with right ventricular dependent single ventricular CHD at the time of a planned Stage II surgical repair. This will be achieved by comparing the data collected in the treatment group (Arm A) to the equivalent data collected in the control group (Arm B), adjusting for baseline.

The concurrent control arm (Arm B) must meet identical study eligibility criteria as the treatment arm (Arm A), except for the requirements related to UCB-MNC product acceptability and DMSO sensitivity. The control arm will undergo the same planned Stage II surgical repair without the investigational cell delivery add-on procedure and will follow-up post-surgery in the same manner as the treatment arm (see Section 6 of this protocol).

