#### **6.3.3 6 Month and Bi-Annual Phone Visits:**

- Changes in Concomitant Medications
- AE Assessment
- Questionnaire Completion (to be completed annually following Stage II surgery)
- Weight

At 6 and 18 months post-Stage II surgery, and every 6 months thereafter for up to 4 years (or until the pre-operative Stage III work-up or cardiac transplant), a phone follow-up with the parent(s) and/or legal guardian(s) will include the collection of the above data. In addition to specific questioning by phone follow-up, medical records should be used for documentation of changes in concomitant medications, AE assessment and subject weight.

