## 7.4 Analysis

### 7.4.1 Interim Analysis

This study has 5 planned safety and efficacy interim analysis planned. An interim analysis will be performed according to statistical analysis plan on all enrolled subjects after 10, 20, 30, 40 and 50 subjects have been treated and completed the 3-month follow-up visit. Results will be reviewed by the DSMB.

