#### **7.4.5 Safety Analysis**

Adverse Events (AEs) will be described by count and frequency, by body system and severity and groups compared using the chi-square test.

The long-term endpoint regarding arrhythmia events and arrhythmia medication will be analyzed regarding safety. Additional adverse events which will be separated out for analyses of their own will be occurrences of bleeding, to such an extent they would be regarded as AEs, decreased cardiac function, and tumor formation.

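### Section 7.4.5 compares adverse events by a plain chi-square with no allowance for follow-up time, although children are followed for different lengths of time and follow-up may differ between arms

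*Combined protocol and SAP*

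**What the plan says.** Section 7.4.5 (Safety Analysis) gives one between-group method for AEs: "Adverse Events (AEs) will be described by count and frequency, by body system and severity and groups compared using the chi-square test". Bleeding, decreased cardiac function and tumor formation are to be analysed separately, but no method is named for them.

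AE assessment starts at enrolment (Section 6.5, note 8) and continues for as long as the child takes part, which the Clinical Study Summary defines as: "Up to 4 years or until pre-operative work-up for Stage III surgical palliation has been completed or until cardiac transplant, whichever is first". Withdrawal, loss to follow-up and death also end it. Section 7.2 admits children to the safety population if they have follow-up data, with no minimum.

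Unequal follow-up is dealt with elsewhere, but not for AEs. The censoring rule in Section 7.3 covers time-to-event analysis, and Section 7.4.4 uses Kaplan-Meier and Cox methods for outcomes such as transplant listing or death.

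On the arms, Section 3.1 says the controls "will follow-up post-surgery in the same manner as the treatment arm". On the looks, Section 7.4.1 says "An interim analysis will be performed according to statistical analysis plan on all enrolled subjects", timed by 10, 20, 30, 40 and 50 treated children reaching 3 months.

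**The concern.** A chi-square on the proportion of children with an AE treats every child as observed for the same time. Variation between children does no harm if its distribution is the same in both arms. If one arm is observed longer on average, that arm shows more children with events even when the event rates are identical.

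The documents give three routes to such a gap:

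- Allocation is not randomised. It depends on product availability and family choice, so nothing balances entry dates or retention.
- Each look is triggered by treated children only but takes in everyone enrolled. Nothing ties control accrual to the trigger. In the earlier Observational study control "recruitment was limited to only three subjects in this time period".
- Follow-up ends at Stage III work-up, transplant or death. The hypotheses in Section 1 include reaching Stage III work-up and "prolonging time to cardiac transplantation or death".

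At stake is how the safety tables are read. The DSMB uses safety endpoints to judge continued enrolment (Section 1) and reviews every interim. Under Section 7.4.2 the Sponsor may decide, any time after the first look, that safety and efficacy endpoints have been met.

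**Working it through.** **The plan's own figure.** Section 7.1 gives detectable effect sizes of 0.57 (50 per arm) and 0.74 (40% attrition, so 30 per arm) at 80% power and alpha 0.05. A two-sided two-sample t-test gives 0.566 and 0.736, so both reproduce. They concern cardiac function. The plan has no corresponding figure for safety.

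**Inputs.** Looks at 10 to 50 treated children (7.4.1) and up to 50 per arm (7.1) come from the plan. Event rates and follow-up gaps are not in the documents and are assumed: a constant first-event rate r of 0.25-1.0 per child-year, the same in both arms, with follow-up of 2.0 v 1.0 or 2.0 v 1.5 years.

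**Formula.** P(at least one AE by time t) = 1 − exp(−r × t). The rejection rate of the uncorrected 2×2 chi-square at two-sided 0.05 is found by exact binomial enumeration.

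**Example, r = 0.5, 50 per arm.**
- 2.0 years: 1 − exp(−1.0) = 63%.
- 1.0 year: 1 − exp(−0.5) = 39%.
- Pooled 0.513; expected z = 0.239 / √(0.513 × 0.487 × 2/50) = 2.39, beyond 1.96. Exact rejection is 69%.
- 1.5 years: 1 − exp(−0.75) = 53%. Against 63%, exact rejection is 19%.
- Equal follow-up: about 5%.

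**False rejection across r = 0.25-1.0, no true difference:**

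| Children per arm | 2.0 v 1.0 years | 2.0 v 1.5 years |
|---|---|---|
| 10 | 11-18% | about 5-6% |
| 20 | 23-41% | about 9-11% |
| 50 | 46-79% | 13-21% |

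With 10 treated and 3 controls, the one-year gap gives 3-20%.

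**Front-loaded events.** Suppose half of the children have a peri-operative AE and the rate afterwards is r. Then P = 1 − 0.5 × exp(−r × t). At r = 0.5 this is 82% at 2.0 years, 70% at 1.0 and 76% at 1.5. Rejection at 50 per arm falls to 29% (one-year gap) and 10% (half-year gap). At r = 0.25 it is 15% and 7%.

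**Masking.** Assume a true doubling of the rate, 0.6 v 0.3 per child-year, with 50 per arm and controls followed for 3 years (59% with an event).
- Treated followed 3 years: 1 − exp(−1.8) = 83%; power 78%.
- Treated followed 2 years: 1 − exp(−1.2) = 70%; power 19%.
- Treated followed 1.5 years: 1 − exp(−0.9) = 59%, the same as controls; rejection 5%, the null level.

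A simulated test of first events over person-time (20,000 runs, constant rates) stayed near 5% in each equal-rate case run, and kept about 76% power in the 1.5 v 3 year case.

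**Unit of analysis.** Section 7.4.5 does not say whether the chi-square counts children or events. In Phase I, two children had 15 + 7 = 22 of 27 SAEs (Section 1.4), so a chi-square on event counts would also ignore clustering within a child.

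**The case against.** The strongest reply is that both arms have the same schedule and the same end points for follow-up, and that no passage states or measures a gap. That stands. A reader might infer that the arms are in fact followed for different lengths of time; the documents do not say so.

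A reader might also infer that the cells shorten follow-up in the treated arm by bringing children to Stage III sooner. The endpoint is success in being scheduled for Stage III, not earlier scheduling, and delaying transplant or death would lengthen follow-up. The net direction is unknown.

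The shortage of controls belongs to an earlier study. Section 1.4 says many eligible families "were unwilling to participate in the Observational study that required multiple non-standard of care clinical visits", and that Phase IIb was designed with fewer such visits for this reason. Later control accrual is a risk, not a forecast. If the study runs until 50 children have completed each arm (Section 7.4.2), staggered entry would largely wash out, though differences in exit time would not.

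The largest error rates belong to 50 per arm, not the early looks, and front-loaded events shrink them. The stopping rules in Section 8.11 use no chi-square p-value: three turn on individual related events within 30 days and the fourth on a pattern of concern. All of this limits the size of the problem. None of it supplies a window or denominator.

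**Conclusion.** The point holds conditionally. The only stated between-group AE test is valid only if follow-up has the same distribution in both arms, and the plan neither secures that nor provides for checking it. If a gap arises, the error can go either way: a one-year gap gives false rejection of 11-18% at 10 per arm, rising to 46-79% at 50, and a doubled rate can disappear. A half-year gap does little at the first look (about 5-6%) and gives 13-21% at 50 per arm. These sizes rest on assumed constant rates and assumed gaps, and are smaller where peri-operative events dominate.

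This should be fixed, but it is not critical. It does not touch the primary endpoint, and no formal safety hypothesis depends on it. It matters because the DSMB, and any Sponsor decision that safety endpoints have been met, may rest on these tables.

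**What to change.** In Section 7.4.5:

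- Report follow-up time by arm beside every AE table.
- Compare the arms by cumulative incidence over fixed windows from Day 0 (30 days, 3 months, 12 months), with children not yet through a window censored and death or transplant treated as competing events.
- Report whole-study AEs as rates per child-year with a rate ratio and 95% CI, from a model that allows repeated events within a child, for example negative binomial with log follow-up time as offset.
- State that the child is the unit for any proportion.
- Use the same tables at each DSMB look.

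Let the fixed windows carry the comparison. With front-loaded events a whole-study rate falls as follow-up lengthens: one peri-operative event per child and none later gives 1/2 = 0.5 per child-year over 2 years but 1/1 = 1.0 over 1 year.

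The cost is SAP wording and modest programming. No new visits or procedures are needed.

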### 3.2 Short Term Endpoints

The primary short-term efficacy endpoint regarding the cell product and its delivery procedure is:

Change in right ventricular cardiac function at 3 months post-Stage II surgery compared to baseline, measured by *apical fractional area change, circumferential strain, and longitudinal strain on echocardiogram*.

Secondary short-term efficacy and safety endpoints in order of their relevance and importance in this clinical study are:

- 1) Change in cardiac function between baseline and hospital discharge for Stage II surgery, measured by echocardiogram.
- 2) Cumulative days of hospitalization per patient at 1 and 3-months post Stage II surgery.
- 3) Change in weight, heart rate, and oxygen saturation at 3-months post Stage II surgery compared to baseline.

Additional variables may be assessed in an exploratory manner.

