### 3.3 Long Term Endpoints

The primary long-term efficacy endpoint regarding the cell product and its delivery procedure is:

Change in right ventricular cardiac function at 12 months post-Stage II surgery compared to baseline, measured by echocardiogram.

Secondary long-term efficacy safety endpoints in their order of relevance and importance in this clinical study are:

- 1) Change in weight every 6 months post-Stage II surgery compared to baseline.
- 2) Change in heart failure medication taken every 6 months post-Stage II surgery compared to baseline.
- 3) Change in arrhythmia medication taken every 6 months post-Stage II surgery compared to baseline.

- 4) Success of subject being scheduled for Stage III surgical repair.
- 5) Time (days) until listed for cardiac transplantation, or death following the 6-month follow-up.
- 6) Change in right ventricular function at Stage III surgery pre-op work-up compared to baseline, obtained by echocardiogram, cardiac MRI, and cardiac catheterization.

Additional variables may be assessed in an exploratory manner.

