## **6.2 Enrollment**

### **6.2.1 Enrollment/Cell Delivery:**

- Procedural Timeout (after completion of Stage II surgery)
- Assessment of Eligibility/Enrollment
- AE Assessment
- Cell delivery (treatment group only)
- Telemetry
- High Sensitivity Troponin T at 3 hour +/- 30 min and 6 hour +/- 30 min after enrollment

A site investigator will assess subject eligibility up to the time of enrollment. If there are new test results or conditions identified up to the time of enrollment that causes a subject to no longer be eligible for participation in this study, the subject will be considered a screen failure.

Adverse events will be recorded in the eCRF and subject's study binder following enrollment to document new or worsening symptoms.

During the hospitalization (starting on Day 0), subjects will be monitored with continuous telemetry from enrollment through discharge (or up to 30 days post-surgery if the subject remains hospitalized). The date and time and the type of any arrhythmias that occur via telemetry that are determined to be clinically significant by a study cardiologist will be recorded in the appropriate eCRF and within the subject's study file.

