## 7 STATISTICAL ANALYSIS PLAN

Sections 3.2 and 3.3 of this protocol provide a full description of the study endpoints.

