## **8.10 Expected Events**

The following are events that may occur as a result of receiving the cell product:

- Mild ventricular tachycardia and/or other mild ventricular arrhythmias
- Mild myocarditis
- Mild pericarditis
- Mild to moderate myocardial infarction
- Mild to moderate pericardial effusion(s)
- Mild to moderate fever for up to 3 days following cell delivery
- Mild to moderate bleeding at the injection site

There are no long-term adverse effects associated with an MRI. There are some potential side effects associated with the general anesthesia required to complete the MRI examination. Most of these are very mild and will go away shortly after the anesthesia care is stopped. The mild side effects include nausea, dizziness, and headache. Other potential risks include, but are not limited to, adverse medication reactions (allergies, etc.), abnormal heart rhythms, low blood pressure or impaired breathing. These more serious problems are very rare, affecting less than 1 in 2000 children.

The risks associated with a Transthoracic Echocardiogram (TTE) include the possibility of mild discomfort associated with placement of the ultrasound transducer on the chest wall while acquiring the echo images. The risks associated with a TTE using moderate (conscious) sedation include possible prolonged sedation, nausea, vomiting and/or a slight risk of allergic reaction. There are no long-term adverse effects associated with the echocardiogram itself.

Repeated or lengthy use of general anesthetic and sedation drugs during surgeries or procedures in children younger than 3 years may affect their brain development.

Intravenous access catheters may be placed as part of sedation/anesthesia for the echoes and MRIs. Placing an IV may cause some pain and bleeding or bruising at the spot where the needle enters the body. Rarely, it may cause fainting. The longer an IV catheter is left in place, the more common it is for redness or infection to develop.

There may be data privacy risks pertaining to the collection of patient data for any study, including this study.

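### Section 7.4.5 analyses arrhythmia through a long-term event endpoint that Sections 3.2 and 3.3 do not define, so arrhythmia in the injection period has no like-for-like comparison between arms

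*Combined protocol and SAP*

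**What the plan says.** Section 7 opens by fixing where endpoints are defined: "Sections 3.2 and 3.3 of this protocol provide a full description of the study endpoints". The only arrhythmia item in those two sections is Section 3.3, item 3: "Change in arrhythmia medication taken every 6 months post-Stage II surgery compared to baseline". Section 3.2 has none. Its nearest item is "Change in weight, heart rate, and oxygen saturation at 3-months post Stage II surgery compared to baseline".

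Section 7.4.5 nevertheless says: "The long-term endpoint regarding arrhythmia events and arrhythmia medication will be analyzed regarding safety". It gives no event definition, data source, time window or method for the event half. It compares AEs in general between groups by chi-square, by body system and severity, and adds separate analyses for bleeding, decreased cardiac function and tumor formation.

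Sections 1.5 and 8.10 list possible effects of the product. The first is "Mild ventricular tachycardia and/or other mild ventricular arrhythmias", and myocardial infarction is also listed.

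Section 6.2.1 schedules continuous telemetry from enrollment to discharge, or to 30 days after surgery for a child still in hospital. The eCRF receives "The date and time and the type of any arrhythmias that occur via telemetry" when a study cardiologist judges them clinically significant. The same section schedules "High Sensitivity Troponin T at 3 hour +/- 30 min and 6 hour +/- 30 min after enrollment". Neither item is restricted to the treatment arm.

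**The concern.** The product is injected once, on Day 0, and arrhythmia is one of four potential harms that Section 1.4 names, with bleeding, cardiac damage and tumor formation. Section 7.4.5 ties arrhythmia to an endpoint that is labelled long-term and is not in the endpoint list. The defined half, medication, cannot fill the gap: under Section 4.7 and footnote 9 of Section 6.5, medication changes during the Stage II hospital stay are not recorded. A drug started and stopped before discharge leaves no trace.

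At stake is whether the trial can say, with equal capture in both arms, how often arrhythmia followed surgery with and without injection. Evaluating safety is part of the stated purpose in Section 2, and the data for this comparison are already collected.

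**Working it through.** The plan gives no rate, precision or power for any safety outcome. Its only sample-size figures (Section 7.1) concern cardiac function and play no part here, though the main one reproduces: 50 per arm and an effect size of 0.57 give 80.6% power by two-sided t-test. The check is therefore a tracing of text, followed by two calculations on assumed rates.

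**1. Tracing the endpoint.** Section 7 points to 3.2 and 3.3. Section 3.2 has no arrhythmia item, and 3.3 has medication only. Section 2 defines long-term as 6 months to 4 years after surgery. Read literally, the arrhythmia sentence in 7.4.5 covers an undefined event and a six-monthly medication measure, both outside the injection period.

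**2. How an acute arrhythmia can reach a comparison.** Section 8.8 records an AE if it is (a) serious, (b) at least possibly related to the study drug or its delivery, or (c) moderate or worse.

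- Serious, or moderate or worse: recorded in either arm.
- Mild and non-serious, treated child: recorded if an investigator judges it at least possibly related.
- Mild and non-serious, control child: criterion (b) cannot in practice be met, because no product was given, so it is not recorded.

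The risk named in Sections 1.5 and 8.10 is mild ventricular arrhythmia, which is the class where the arms are captured differently. The telemetry record in 6.2.1 depends neither on relatedness nor on AE grade, and enrollment occurs at the Procedural Timeout in both arms (Section 4.3), so observation starts at the same point.

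**3. Size of the differential capture.** Let m be the true proportion of children with a mild, non-serious but clinically significant arrhythmia, equal in both arms, and f the share judged at least possibly related in treated children. Expected AE-table counts are 50·m·f treated and 0 control. Telemetry would show 50·m in each. The documents give neither quantity. Assume m = 20%, so 50 × 0.20 = 10 children per arm:

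| f | AE table, treated | AE table, control | Telemetry, each arm |
|---|---|---|---|
| 0 | 0 | 0 | 10 |
| 0.5 | 5 | 0 | 10 |
| 1 | 10 | 0 | 10 |

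For m from 10% to 30%, telemetry would show 5 to 15 per arm. At f = 0.5 the AE table would show 2.5 to 7.5 treated against 0. The distortion can run either way: a spurious excess when f is high, or a real excess unseen when f is near zero.

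**4. What a telemetry comparison would deliver.** For a common rate p and n per arm, the 95% half-width for the risk difference is 1.96·√(2p(1−p)/n).

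- n = 50: p = 0.1 gives 1.96 × √(0.18/50) = 11.8 points; p = 0.2 gives 15.7; p = 0.3 gives 18.0.
- n = 30, the lower planned size: p = 0.1 gives 1.96 × √(0.18/30) = 15.2 points; p = 0.2 gives 20.2; p = 0.3 gives 23.2.
- No events among treated children: the exact two-sided 95% upper limit is 1 − 0.025^(1/n), which is 7.1% for 0/50 and 11.6% for 0/30.

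Using n = [1.96√(2p̄(1−p̄)) + 0.84√(p₁(1−p₁)+p₂(1−p₂))]²/(p₂−p₁)², with p̄ the mean of the two rates, 50 per arm has 80% power only for about 5% against 24.7%, 10% against 32.7%, or 20% against 46.1%. An interval is therefore more informative than a test.

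**5. Troponin.** It is drawn at baseline (6.1.1) and at 3 and 6 hours (6.2.1) in both arms. Section 7 does not name it. Section 7.3 offers descriptive statistics as appropriate for all variables, but commits to a by-group description only for baseline values.

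**The case against.** The strongest reply is that arrhythmia is not omitted. Section 7.4.5 names arrhythmia events, and its next sentence introduces bleeding and the rest as additional, which implies that arrhythmia already has its own analysis. Acute events also reach the AE chi-square: anything serious, moderate or worse, or possibly related is recorded, and Section 5.4.2 requires an event that halts the injections to be recorded as an AE. Troponin falls under the descriptive statistics of 7.3, and Section 8.1.1 allows an abnormal laboratory finding to be an AE. Injection-site bleeding, the one AE that Section 1.4 reports as definitely related to delivery, does have its own analysis.

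All of this stands, and it limits the point. A reader might infer that acute arrhythmia and troponin enter no analysis, that the data are left unused, or that the arrhythmia conclusion rests on six-monthly medication alone. The documents do not support those readings. Nor does troponin's absence from Section 7 follow from the endpoint mismatch; it is a separate and smaller gap.

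The reply does not supply an event definition, a source or a window for the injection period. Nor does it make the AE route symmetric for mild events.

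It is also fair that the timing of arrhythmia is an inference: Sections 1.5 and 8.10 give a time limit only for fever. The case for an early window rests on the single Day 0 injection and on the monitoring that the protocol itself schedules.

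**Conclusion.** The point holds in this form: the arrhythmia-event outcome in 7.4.5 is undefined and labelled long-term, and the remaining route for acute arrhythmia, the AE table, does not capture mild events alike in the two arms. The part of the arrhythmia burden affected is mild, non-serious events judged clinically significant on telemetry. More severe events are captured in both arms, although the table groups them by body system with other events after open-heart surgery.

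The size depends on rates that the documents do not give. At an assumed 20% in each arm of 50, equal true risk could appear as anything from 0 against 0 to 10 against 0. A telemetry comparison at assumed rates of 10 to 30% would carry a half-width of about 12 to 18 points with 50 per arm, and about 15 to 23 points with 30. That can exclude only a large excess, but it counts the same thing in both arms.

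The gap for troponin is narrower: values are collected in both arms, and what is missing is a specified by-arm summary.

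**What to change.** In Section 7.4.5, replace the arrhythmia sentence with wording to this effect:

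- The arrhythmia-event safety outcome is any clinically significant telemetry arrhythmia recorded under Section 6.2.1 from enrollment to discharge, or to Day 30 if the child is still in hospital. The number and percentage of children with at least one event will be given by arm, overall and by type, with the risk difference and 95% CI, regardless of relatedness or AE grade.
- Change in arrhythmia medication (Section 3.3, item 3) is the longer-term measure.
- High-sensitivity troponin T at 3 and 6 hours will be summarised by arm alongside the baseline value.

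Add the event outcome to Section 3.2 as a safety outcome, so that Section 7's reference to the endpoint sections is true. A baseline-adjusted troponin model and separate tables for the other events in Section 8.10 are optional.

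The cost is SAP wording and a few tables, with no new visits or samples. Three limits should be stated with the results. Clinical significance is judged by cardiologists in an open-label study. The arms are not randomised and may differ in operative course, which baseline troponin does not correct. The window varies with length of stay, so telemetry days should be shown by arm. The comparison is descriptive.
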